6. DOSING DELAYS/DOSE MODIFICATIONS

Dose delays and modifications will be made as indicated in the following table(s). The descriptions and grading scales found in the revised NCI Common Terminology Criteria for Adverse Events (CTCAE) version 5.0 will be utilized for dose delays and dose modifications. A copy of the CTCAE version 5.0 can be downloaded from the CTEP website http://ctep.cancer.gov/protocolDevelopment/electronic_applications/ctc.htm.

Neurologic toxicities per CTCAE v5.0 probably or definitely related to protocol therapy (not applicable to toxicities/symptoms secondary to intracranial tumor burden)	
grade 1 or 2	Continue radiation / AGuIX administrations
grade 3	Hold radiation / AGuIX administrations until \leq grade 2, then continue both radiation and AGuIX administrations
grade 4	Hold radiation 1 week and until \leq grade 2, then continue (no further AGuIX will be administered)

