Incidence of renal failure not assessed because data are extrapolated from animal studies with AGuIX. A study in rats (reference Wil Research AB20679) showed the reversibility of the minimal tubular vacuolation phenomenon observed during drug elimination, after a recovery period of 10 weeks, following 2 IV injections at a high dose of 750 mg/kg (HED = 121 mg/kg).

Data from the Nano-Rad phase I clinical trial:

Summary of all serious adverse events (SAE):

Preferred term	Total	Possibly related*
Eye disorders		
Blindness	1	
Gastrointestinal disorders		
Oesophagitis	1	

General disorders and administration site conditions		
Cardiac death	1	
Disease progression	7	
General physical health deterioration	1	1
Infections and infestations		
Device related infection	1	
Sepsis	1	
Injury, poisoning and procedural complications		
Craniocerebral injury	1	
Delayed effects of radiation	1	1
Neoplasms benign, malignant and unspecified (incl cysts and polyps)		
Malignant neoplasm progression	4	
Malignant pleural effusion	2	
Neoplasm progression	1	
Nervous system disorders		
Epilepsy	1	
Intracranial pressure increased	1	
Leukoencephalopathy	1	1
Partial seizures	1	
Psychiatric disorders		
Confusional state	2	1
Respiratory, thoracic and mediastinal disorders		
Pulmonary embolism	2	

*These SAEs were related to radiotherapy and were considered as possibly related to study drug by the Sponsor, as AGuIX acts as a radiosensitizing agent.

Summary of non-serious adverse events:

Preferred Term	Total	Possibly/Probably linked to AGuIX	Low intensity	Moderate intensity
Blood and lymphatic system disorders				
Anaemia	1		1	
Thrombocytopenia	2		2	
Cardiac disorders				
Supraventricular extrasystoles	1			1
Ear and labyrinth disorders				
Hypoacusis	1		1	
Vertigo	1		1	
Endocrine disorders				
Hypothyroidism	1		1	
Gastrointestinal disorders				
Aphthous ulcer	1			1
Constipation	2			2
Diarrhea	1		1	
Nausea	6	1	4	2
Vomiting	2		2	
General disorders and administration site conditions				
Asthenia	4		1	3

Gait disturbance	1			1
Malaise	1			1
Pain	1		1	
Pyrexia	1			1
Infections and infestations				
Sinusitis	1			1
Metabolism and nutrition disorders				
Hypoglycaemia	1			1
Musculoskeletal and connective tissue disorders				
Musculoskeletal pain	1			1
Nervous system disorders				
Aphasia	1			1
Balance disorder	1			1
Cerebellar syndrome	1	1		1
Cognitive disorder	1		1	
Disturbance in attention	1		1	
Dysmetria	1		1	
Headache	6	2	3	3
Hemiplegia	1			1
Intracranial pressure increased	3	1	2	1

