
The length of follow up for the neurocognitive secondary endpoint will also be 12 months. The length of follow up for all other endpoints will be until censoring or death. Of note, the usual clinical care for patients with brain metastases involves a radiation oncology visit, history, and an MRI brain every 1.5-3 months until death or other loss to follow up. All secondary endpoints (with the exception of neurocognition and health status) are assessed as part of usual clinical care. Patients can elect to follow-up with a local provider following the completion of radiation if deemed appropriate by the study PI, in which case brain imaging must be retrieved and digitally stored. Providers will call patients whom elect to follow-up with a local provider to discuss imaging results and complete study documentation; in such cases quality of life testing and neurocognition do not need to be pursued.

Study calendars are presented here:

Patients managed with SRS

	Baseline ^a	Radiation Planning	2-5 Days Before Radiation Initiation	Radiation Day 1 ^b	Follow Up ^c	eDC Timepoints
Informed consent	X					
Medical history	X				X	Baseline
Karnofsky performance status	X				X	Baseline, Follow-up
CT simulation		X				Pre-Radiation
MRI brain			X ^d		X	Pre-Radiation, Follow-up
SRS				X		Radiation
AGuIX or placebo administration			X	X		Pre-Radiation, Radiation
Quality of life assessment	X				X	Baseline, Follow-up
Health status assessment	X				X	Baseline, Follow-up
Neurocognitive Assessment	X				X ^e	Baseline, Follow-up
Volumetric imaging	X				X	Baseline, Follow-up
AE assessment ^f	X		X ^g	X ^g	X	Baseline, Pre-Radiation, Radiation, Follow-up

Abbreviations: AE=Adverse Event; AGuIX=Activation and Guidance of Irradiation by X-ray; CT=Computed Tomography; MRI=Magnetic Resonance Imaging; SRS=Stereotactic Radiosurgery; SRT=Stereotactic Radiotherapy

a. Within 21 days

b. Within 14 days of radiation planning MRI

c. Follow up visits occur post radiation at approximately 1.5/3/5/7/9 months, and every 3 months thereafter (+/- 4 weeks except 1.5 month visit which is +/- 1 week)

d. To be performed before and after administration of AGuIX vs placebo

e. Neurocognitive assessments occur in the follow up period at 3 months and 12 months

f. For the purpose of this protocol, acute adverse events collected and documented on CRFs are only acute non-hematologic grade 3 or higher toxicities that did not predate radiation and are possibly, probably or definitely related to radiation/AGuIX

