In addition, we utilize a second early stopping rule applicable to the entire cohort. If two or more of the first six patients randomized to receive AGuIX display an acute, grade 3-5 non-hematologic toxicity within 1.5 months of the end of protocol-based treatment that is possibly, probably, or definitely related to AGuIX administration the study will be closed to further enrollment. If the true rate of such toxicity is 33%, then there is a 65% chance that at least two of the first six patients would experience it. If this early stopping rule is met, then any plans to re-open the study with a modified treatment plan will need to be formally reviewed and approved by the sponsor and by the DF/HCC SRC/IRB prior to activation. If there are less than two instances of acute, grade 3-5, non-hematologic toxicity within 1.5 months of the end of protocol-based treatment that are possibly, probably, or definitely related to AGuIX administration among the first six patients, the study will proceed to full accrual. Of note the first post-treatment assessment will occur at 1.5 months. Case report forms for such patients will be monitored weekly by the unblinded CRC until either the early stopping rule is met or it is determined that the early stopping rule cannot be met.

The study will incorporate an early stopping rule for futility. After 50% of the total patient accrual (that is, 67 of the 134 patients) have been observed through 9 months, we will evaluate the best intracranial response rate (iRR) achieved over 9 months for the pre-specified futility analysis. It is expected that the control iRR rate is on the order of 70% and the experimental iRR rate will be improved to at least 86%. Under this scenario, the overall study has 83% power for this comparison at full information (98 intracranial responses) using a one-sided 0.10 level test of proportions. For 50% information time on iRR (49 intracranial responses), it is projected that this will be reached roughly at study month 26, given an expected accrual of 47-48 patients per year, 17 months of accrual and 9 months follow-up for the first 67 patients. The Wieand rule will be used to assess futility. If the iRR is higher the experimental arm the study will proceed to full accrual. If the iRR is high in the non-experimental/placebo arm we will examine local control on

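### The study-wide toxicity stopping rule counts events by their relation to AGuIX alone and does not say how radiation-attributed events in AGuIX patients are counted

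*Protocol*

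**What the plan says.** Section 13.4 gives the one toxicity stopping rule that covers the whole cohort: "If two or more of the first six patients randomized to receive AGuIX display an acute, grade 3-5 non-hematologic toxicity", where the event falls in a window closing 1.5 months after treatment ends and is "possibly, probably, or definitely related to AGuIX administration the study will be closed to further enrollment". The sentence that lets the study continue repeats the AGuIX-only attribution. The operating characteristic is given as "If the true rate of such toxicity is 33%, then there is a 65% chance that at least two of the first six patients" would have such an event. The data source is also fixed: "Case report forms for such patients will be monitored weekly by the unblinded CRC".

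The footnotes to all three calendars in section 10 define which acute events reach the CRF: non-hematologic, grade 3 or higher, and such that they "did not predate radiation and are possibly, probably or definitely related to radiation/AGuIX". Section 7.2 defines the attribution categories, from unrelated to definite, against study treatment without separating the agent from the radiation.

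Section 7.1 reports how the earlier trials handled the question. Under the Nano-Rad table of serious events, a footnote to the possibly related column reads "These SAEs were related to radiotherapy and were considered as possibly related to study drug by the Sponsor", on the ground that AGuIX is a radiosensitizer. The NANORAD2 table carries a similar footnote for one event. Section 5.1 states that patients and investigators are blinded to the infusion.

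**The concern.** Section 2.3 gives the mechanism: AGuIX is infused to increase the effect of radiation in the treated volume. Harm that works through this mechanism would look like radiation injury. A blinded clinician who sees acute in-field swelling after stereotactic treatment can reasonably call it radiation toxicity. The event then meets the CRF criterion, but whether it meets the stopping rule depends on how the word possibly is read when the named cause is AGuIX administration.

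The rule is one count with a threshold of two in six, so a single event attributed differently can reverse the decision. With fewer than two events the trial goes to full accrual, and no later study-wide toxicity rule is given. The other toxicity rule in 13.4 covers only the two prior-radiation strata and only necrosis that requires resection. Section 13.3 caps each of those strata at 22 patients, so at least 134 − 2 × 22 = 90 patients would fall outside them.

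**Working it through.** **Step 1. The attribution bases side by side.**

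| Place in protocol | Purpose | Basis |
|---|---|---|
| 7.2 | Attribution scale | Study treatment |
| 10, calendar footnotes | Which acute events are documented on the CRF | Radiation/AGuIX |
| 13.4, study-wide rule | Which events count toward two of six | AGuIX administration |
| 7.1, earlier-trial footnotes | How the marked radiotherapy-related serious events were classed | Possibly related to study drug |

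Nothing in the protocol maps one row to another. In the earlier trials the sponsor made the step from radiotherapy-related to possibly drug-related. Section 13.4 assigns that step to nobody.

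One Nano-Rad entry shows why this matters. Section 2.3 reports one acute in-field grade 3 toxicity, raised intracranial pressure. The serious event of that name in 7.1 has no possibly related mark. That the two are the same event is an inference.

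**Step 2. Reproduce the stated figure.** Let X be the number of counted patients among six, binomial with rate p. Then

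P(X ≥ 2) = 1 − (1 − p)^6 − 6p(1 − p)^5.

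- p = 0.33: 1 − 0.0905 − 0.2673 = 0.642.
- p = 1/3: 1 − 64/729 − 192/729 = 473/729 = 0.649.

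The stated 65% is right.

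**Step 3. Let part of the toxicity be attributed to radiation only.** Suppose the true rate of acute grade 3-5 toxicity is 1/3 and a share f of it is recorded as at least possibly related to AGuIX. The counted rate is f/3. The documents give no value for f, so a range is shown.

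| f (assumed) | Counted rate | P(X ≥ 2) |
|---|---|---|
| 1.00 | 0.333 | 65% |
| 0.90 | 0.300 | 58% |
| 0.75 | 0.250 | 47% |
| 0.50 | 0.167 | 26% |
| 0.25 | 0.083 | 8% |

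For f = 0.50: 1 − (5/6)^6 − (5/6)^5 = 1 − 0.335 − 0.402 = 0.263.

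**Step 4. The price of a wider count.** If radiation-related events count, background toxicity from radiation alone can trigger the rule. With no AGuIX effect and a background rate b (assumed, since the documents give none):

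- b = 5%: P(X ≥ 2) = 3.3%.
- b = 10%: 11.4%.
- b = 15%: 22.4%.

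Section 7.1.1 lists the serious immediate reactions to stereotactic radiation, such as symptomatic brain swelling, as rare or extremely rare. That points to the lower end of this range.

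**The case against.** The strongest reply is that such events would be counted anyway. Possibly is a low bar, section 7.2 defines it as an event that may be related, and a blinded investigator who knows the agent is a radiosensitizer cannot easily exclude it. The convention is printed in this protocol's own adverse event section. This is a fair reading, and many events may be handled this way. But 13.4 does not require it, and the footnotes describe what a sponsor did in other trials.

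A second reply is that an agent-specific basis is a legitimate choice. Radiation here is standard care, the rule has no comparator, and a wider count brings in background events. That cost is real and is shown in step 4. It is an argument for choosing the basis openly; it does not settle how a radiation-attributed event should be treated.

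Third, there are backstops. Section 7.3 requires expedited reporting of most grade 4 and all grade 5 events even if unrelated, and the DSMB reviews toxicity twice a year. These are partial: at 47-48 patients a year, about 24 could enrol between meetings.

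Some stronger inferences do not hold:

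- A reader might infer that the CRF has one pooled attribution field, so that AGuIX-related events cannot be picked out. The footnotes are a collection filter; separate fields are neither stated nor excluded. On attribution the filter is wider than the rule, so any omission would come from the rule's wording.
- A reader might size the problem from the four Nano-Rad serious event entries marked possibly related, among 15 patients. Entries are not patients, some were late, the radiation was whole-brain, and all four carry the relatedness category that the rule counts.
- A reader might add the dose-hold table in section 6, which uses events "probably or definitely related to protocol therapy". That table guides treatment of an individual patient, and a different basis there is no contradiction.

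**Conclusion.** The point stands as a defect of moderate weight in the definition of the counted event. The rule, the CRF criterion and the attribution scale name three different causes, and nothing says how a radiation-attributed event in an AGuIX patient enters the count of two in six.

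The 65% figure is not wrong. A reader might infer that it belongs to no defined event, but 13.4 defines the event by grade, type, window and attribution, and the figure follows for a 33% rate of events so counted. What is unsettled is how much of the true toxicity becomes a counted event. At a true rate of one in three, the chance of stopping is 47% if 75% of it is attributed to AGuIX and 26% if 50% is. Both shares are assumptions that show sensitivity; they are not estimates. It does not follow that radiation toxicity will be missed, only that the text permits it.

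**What to change.** Reconcile sections 7.2, 10 and 13.4 on one attribution basis, and state in 13.4 how an event attributed to radiation in a patient given AGuIX is counted. The basis that matches the existing CRF criterion and the earlier-trial convention is at least possibly related to radiation and/or AGuIX. If the sponsor prefers to keep the AGuIX-only wording, a sentence saying that radiation-attributed events in AGuIX patients are taken as possibly related would do the same work. Then tie the 33% and 65% sentence to that count.

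The change is to wording. The CRF criterion already covers radiation-related events, and sample size and the efficacy analysis are untouched. The cost is a somewhat higher chance of stopping on background radiation toxicity, about 3% at an assumed 5% background rate and 11% at 10%. The protocol should state that cost next to the 65%.

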12.2. Data Safety Monitoring

The DF/HCC Data and Safety Monitoring Board (DSMB) will review and monitor study progress, toxicity, safety and other data from this study. The Board is chaired by a medical oncologist from outside of DF/HCC and its membership composed of internal and external institutional representation. Information that raises any questions about participant safety or protocol performance will be addressed by the Sponsor-Investigator, statistician and study team. Should any major concerns arise, the DSMB will offer recommendations regarding whether or not to suspend the study.

The DSMB will meet twice a year to review accrual, toxicity, response and reporting information. Information to be provided to the DSMB may include: participant accrual; treatment regimen information; all adverse events and serious adverse events reported across all sites by category; summary of any deaths on study; audit results; and a summary provided by the study team. Other information (e.g. scans, laboratory values) will be provided upon request.

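### The study-wide toxicity rule is one look at six AGuIX patients: at the 33% rate used to describe it, it clears the trial for full accrual 35-36% of the time, and no later study-wide numerical boundary follows.

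*Protocol*

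**What the plan says.** Section 13.4 of the protocol has two toxicity rules. Only the second covers everyone: "we utilize a second early stopping rule applicable to the entire cohort". Its trigger reads "If two or more of the first six patients randomized to receive AGuIX display an acute, grade 3-5 non-hematologic toxicity within 1.5 months". That window is counted from completion of protocol treatment, and the event must be at least possibly related to AGuIX. If the trigger is met, enrolment closes. With fewer than two events "among the first six patients, the study will proceed to full accrual".

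The rule has one stated operating characteristic: at a true rate of 33%, "there is a 65% chance that at least two of the first six patients would experience it". The review behind it is limited in time: "Case report forms for such patients will be monitored weekly by the unblinded CRC until either the early stopping rule is met". It also ends once the trigger can no longer be reached.

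The first rule in 13.4 concerns symptomatic necrosis requiring resection. It applies only to the two prior-radiation strata combined and is also based on a first-six count. The remaining interim rules, in 13.1 and 13.4, concern efficacy and futility.

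After the first six patients, general oversight is in section 12.2: "The DSMB will meet twice a year to review accrual, toxicity, response and reporting information". The DSMB may recommend suspending the study if major concerns arise; no numerical toxicity threshold is given. Expedited and FDA reporting continue under 7.3 and 7.5. Section 13.2 plans about 67 patients per arm.

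**The concern.** Zero or one event in six patients is weak information about a toxicity rate, yet the protocol attaches a definite action to it: the trial goes to full accrual and the rule ends. If the true rate of acute grade 3-5 toxicity were near the figure used to describe the rule, the trial would pass this look in more than one case in three. Roughly ten times as many patients would then receive AGuIX with no pre-set count that obliges anyone to look again.

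This matters more because prior exposure is limited. Section 7.1 says that few patients have received the agent, and the phase I experience in 2.3 is 15 patients given whole brain rather than stereotactic radiation. The first six patients also cannot represent all seven strata, and nothing in 13.4 requires them to include both the two-infusion (SRS) and three-infusion (SRT) schedules of section 5.1.

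**Working it through.** **Inputs.** Close if X ≥ 2 among n = 6 AGuIX patients, evaluated at p = 33% with a stated 65% chance (13.4). About 67 AGuIX patients are planned (13.2). X is taken as binomial(6, p), with independent patients and a common rate.

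**1. The protocol's figure.** P(X ≥ 2) = 1 − (1−p)^6 − 6p(1−p)^5.
- p = 0.33: 1 − 0.0905 − 0.2673 = 0.642.
- p = 1/3: 1 − 0.0878 − 0.2634 = 0.649.

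The stated 65% is reproduced, so there is no arithmetic error.

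**2. Chance of clearance (0 or 1 of 6).** This is the complement.

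| True rate | Cleared for full accrual |
|---|---|
| 10% | 0.886 |
| 20% | 0.655 |
| 25% | 0.534 |
| 30% | 0.420 |
| 33% (1/3) | 0.358 (0.351) |
| 40% | 0.233 |
| 50% | 0.109 |

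The chance of clearance falls below 20% only once the true rate exceeds about 42%.

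**3. What a clearing result rules out.** Exact one-sided 95% upper limits:
- 0 of 6: 1 − 0.05^(1/6) = 0.393.
- 1 of 6: the p solving (1−p)^6 + 6p(1−p)^5 = 0.05, which is 0.582.

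Both exceed 33%.

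**4. Patients beyond the rule.** 67 − 6 = 61, so the rule covers 6/67 = 9% of the arm. At a 33% rate, about 61 × 0.33 = 20 of the later patients would be expected to have a qualifying event.

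**5. Carrying the count forward.** Illustration only; the looks and cut-offs are assumptions. Cumulative counts are read at 6, 12, 24, 36, 48 and 60 AGuIX patients, with cut-offs of 2, 5, 8, 11, 14 and 17. The probability of crossing at any look comes from exact recursion on the binomial count, removing paths that have already crossed.

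| True rate | Six-patient look alone | With later looks |
|---|---|---|
| 10% | 0.114 | 0.115 |
| 20% | 0.345 | 0.411 |
| 25% | 0.466 | 0.639 |
| 33% | 0.642 | 0.922 |

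At 33% the look-by-look crossing probabilities are 0.642, 0.027, 0.098, 0.073, 0.049 and 0.032, which sum to 0.92. At 10% the later looks add about 0.001.

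**The case against.** The case for the plan is substantial. The 65% is disclosed and correct, and an early six-patient check followed by DSMB oversight is a recognisable design. The six patients are not the only safety information: section 2.3 reports phase I escalation with one acute in-field grade 3 toxicity and no in-field grade 4, and section 7.1 tabulates serious events from a randomized phase II trial (41 with whole brain radiation alone, 21 with AGuIX added; denominators not given). The qualifying event needs only possible attribution and has no control-arm comparison, so an automatic later boundary could close a placebo-controlled trial because of radiation or tumour effects.

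Most of this stands, and it limits the point. Three stronger readings are tempting, and the protocol does not support them:
- *That 33% is the rate the protocol regards as unacceptable.* It is only the rate at which the rule is described: "If the true rate of such toxicity is 33%, then there is a 65% chance that at least two of the first six patients would" meet the trigger. No unacceptable rate is declared.
- *That no quantitative toxicity rule can touch any later patient.* The necrosis rule counts the first six AGuIX patients in the prior-radiation strata, who need not be the first six in the study. It covers a different event and is also a first-six rule.
- *That nothing could stop the trial after the first six.* The DSMB can recommend suspension, adverse events are assessed through follow-up, and expedited and FDA reporting continue.

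What the objection does not supply is a number. None of these routes says what cumulative count in the AGuIX arm should prompt a decision. The prior data come from whole brain radiation and do not fill that gap.

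**Conclusion.** The concern holds as a weakness of design, not as an error or contradiction. The only study-wide toxicity rule is a single look at six patients. It clears the trial 35-36% of the time at the one rate the protocol uses to describe it, and more often at any lower rate. Neither clearing result excludes that rate, and about 61 of 67 AGuIX patients are then treated with no study-wide numerical toxicity boundary. Oversight continues without a threshold.

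The probabilities assume independent patients with a common event rate and complete ascertainment within the 1.5-month window. The forward-looking gain depends on the assumed looks and cut-offs. The protocol fixes the trigger, its operating characteristic and the consequence of passing, so this is not detail left to an analysis plan. An amendment is worth making; the trial is not invalid without it.

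**What to change.** In section 13.4, keep the six-patient look, but replace the statement that the study then goes to full accrual with continued cumulative monitoring of the same event across the whole AGuIX arm. The sponsor should:
- state the toxicity rate it wants to detect;
- choose the looks and cut-offs, with the last look late enough to cover essentially the whole arm;
- report the crossing probability at that rate and at low and intermediate rates;
- have the unblinded coordinator give counts by arm to the DSMB;
- make a crossing at a later look a trigger for DSMB review with the placebo-arm rate shown, rather than an automatic closure.

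The schedule in the working is an illustration of the gain, not a proposed rule.

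**Cost.** Protocol wording and further tabulations. No patients or procedures are added, and the study calendar footnotes already require acute non-hematologic grade 3 or higher related toxicities on the CRFs. Section 4.1 gives the unblinded coordinator no further role once the infusion is arranged, so it should be aligned with the monitoring role in 13.4. The statistical price is more crossings at intermediate rates: 34% to 41% at a 20% rate and 47% to 64% at 25%, against almost no change at 10%. Showing the placebo rate at each later crossing limits the harm from those extra crossings.

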One interim analysis for efficacy using a stratified, clustered log rank test will be conducted at 50% information time for the primary endpoint of local recurrence projected to occur roughly 6 months prior to the end of full accrual (study time 2.3 years). An O'Brien-Fleming boundary function will be used at that time to control type I error. If this rule is met, further study accrual will halt but patients already enrolled will be followed.

The randomization will be stratified as outlined below. If 2 or more potential strata could apply to a given patient, the enrolling clinician can select the stratum that is most appropriate.

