a per metastasis level before abandoning the study. If local control on a per metastasis level is also better in the non-experimental/placebo arm then the study will be abandoned. If local control is better in the experimental arm the study will proceed to full accrual. The interim analysis for efficacy based on local control is described above in section 13.1.

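### The futility rule continues the trial on a numerically higher response rate alone, so it stops only about a quarter to just over a third of null trials and has weak power to stop for worse local control unless response is also worse

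*Protocol*

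**What the plan says.** Section 13.1 makes per-metastasis local control the primary endpoint. Section 13.4 bases futility on another endpoint: "we will evaluate the best intracranial response rate (iRR) achieved over 9 months for the pre-specified futility analysis". The timing is given as "After 50% of the total patient accrual (that is, 67 of the 134 patients) have been observed through 9 months", projected at about study month 26. The plan expects that "the control iRR rate is on the order of 70" percent and that "the experimental iRR rate will be improved to at least 86" percent. It names the method: "The Wieand rule will be used to assess futility".

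The decision steps follow in the same section:

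- iRR higher with AGuIX: "If the iRR is higher the experimental arm the study will proceed to full accrual". No margin is set and local control is not examined.
- iRR higher with placebo: local control is examined. "If local control on a per metastasis level is also better in the non-experimental/placebo arm then the study will be abandoned". If local control favours AGuIX, the trial goes on.
- iRR tied: not addressed.

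Section 13.1 has the only other planned interim comparison of local control: "One interim analysis for efficacy using a stratified, clustered log rank test will be conducted at 50% information time". It is projected at study year 2.3 and has an O'Brien-Fleming efficacy boundary. It has no futility or harm criterion.

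**The concern.** Taken together, the steps abandon the trial only when iRR and local control both favour placebo. Local control can rescue the trial after a poor iRR, but it can never stop the trial by itself. If AGuIX leads on iRR by a single response, accrual runs to the end whatever local control shows. The efficacy look, under two months later, does not close this gap because it can only stop for benefit.

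If response and durable control diverge, the endpoint that does not decide the trial overrides the one that does. Anyone who sees the Wieand rule named will also expect its usual behaviour, which is stopping about half of null trials at half information. The added second condition removes a good part of that.

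**Working it through.** **Inputs from the protocol.** 67 patients at the look, 1:1, so 33/34 per arm; control iRR 70%, AGuIX iRR 86%; one-sided 0.10; design hazard ratio (HR) 0.60 with 90% power; 47 to 48 patients per year; 134 in total.

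**Assumptions, not in the protocol.** Correlation rho between the iRR difference and the local-control difference: 0 to 0.7. Effective events behind the local-control comparison at the look: 25 to 50. The upper figure is half of the Schoenfeld total, 4(1.2816 + 1.2816)²/(ln 0.60)² = 26.28/0.2609 ≈ 101; the lower one allows for clustering and immaturity.

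**Step 1. The plan's own figure.** A pooled two-proportion test with 67 per arm, 70% against 86%, one-sided 0.10, gives power 0.8345. The stated 83% is reproduced.

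**Step 2. Ceiling on stopping.** The rule cannot stop unless iRR is lower with AGuIX (ties aside), so P(iRR lower) caps the stopping probability however bad local control is. Exact binomial comparison, control iRR 70%:

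| True AGuIX iRR | 33 control / 34 AGuIX | 34 control / 33 AGuIX |
|---|---|---|
| 70% | 0.479 | 0.521 |
| 78% | 0.206 | 0.247 |
| 80% | 0.152 | 0.189 |
| 86% | 0.044 | 0.063 |

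These caps need no assumption about correlation or event numbers. With 33/33 and equal rates, 10.7% of trials would tie.

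**Step 3. Stopping with no effect on either endpoint.** For two symmetric signs, P(both favour placebo) = 1/4 + arcsin(rho)/(2π). The second row uses the exact 33/34 value of 0.479 in a bivariate normal.

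| rho | 0 | 0.3 | 0.5 | 0.7 |
|---|---|---|---|---|
| Symmetric formula | 0.250 | 0.298 | 0.333 | 0.373 |
| 33/34 split | 0.239 | 0.288 | 0.323 | 0.362 |

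The range is about 24% to 37%; the reverse split adds about two points to the 33/34 row. A sign rule on one endpoint stops about 50%. The two-condition rule reaches that only at rho = 1.

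**Step 4. Stopping when local control is worse.** P(local-control estimate favours placebo) = Φ(ln HR × √(d/4)), with d effective events. For HR 1.67 (the inverse of 0.60): d = 25 gives Φ(0.511 × 2.5) = 0.899; d = 50 gives Φ(0.511 × 3.54) = 0.965. Combined with iRR (33/34 split, rho 0 to 0.7, d 25 to 50):

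| True iRR, AGuIX vs control | HR 1.67: rule as written | HR 1.67: sign of local control alone |
|---|---|---|
| 78% vs 70% | 0.19 to 0.21 | 0.90 to 0.97 |
| 70% vs 70% | 0.43 to 0.48 | 0.90 to 0.97 |
| 60% vs 70% | 0.72 to 0.79 | 0.90 to 0.97 |

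**Step 5. Cost of a sign rule on local control at half information.** The drift at full information is 1.2816 + 1.2816 = 2.563, so at half information the mean is 2.563 × √0.5 = 1.812. P(estimated HR above 1 when the true HR is 0.60) = Φ(−1.812) = 0.035. Power is P(Z at half > 0 and final Z > 1.2816), with correlation √0.5. It equals 0.888, against 0.900 without the rule.

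**Step 6. Patients who could be spared.** At 47.5 per year, month 26 gives 47.5 × 26/12 ≈ 103 enrolled, leaving 134 − 103 = 31. Year 2.3 gives 47.5 × 2.3 ≈ 109, leaving 25.

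**The case against.** The strongest reply is that the rule is deliberate. The Wieand rule is named within an iRR analysis, and the next sentences spell out the safeguard: an unfavourable iRR sign leads to a check of local control before the trial is given up. In a signal-finding phase II study, a lenient futility rule is a legitimate choice. The monitoring board also meets twice a year, sees response and toxicity data and can recommend suspension (section 12.2). Few patients remain to be spared, and a tighter rule costs power.

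Much of this stands, and it limits what can be claimed. A reader might draw three stronger conclusions, which the protocol does not support:

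- **That the rule stops one null trial in four.** This holds only near zero correlation. Response and local control are both assessed on the radiated lesions of the same patients (section 11.1), so positive correlation is likely and the figure rises to about 37% at rho 0.7.
- **That the rule cannot detect worse local control.** When response is also clearly worse, it stops about 72% to 79% of trials. The weakness is confined to iRR being equal or better with AGuIX.
- **That the plan breaks a promise to run a Wieand rule on local control.** It makes no such promise. It applies the rule to iRR and then weakens it with the local-control override.

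The reply does not justify the first branch. A safeguard against wrongly stopping explains why local control is checked when iRR is poor. It does not explain why local control is ignored when iRR is good. The board has no numerical rule to fill that gap.

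**Conclusion.** The concern holds in a limited form. Under section 13.4 the primary endpoint cannot stop the trial unless iRR already points the wrong way, and no other planned look can stop for unfavourable local control.

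The ceilings of about 50% (equal iRR) and 15% to 25% (iRR 78% to 80% against 70%) follow from the protocol's sample size and control rate, given those true AGuIX rates. The null range of 24% to 37% also depends on the assumed correlation, and the harm figures on the assumed correlation and event numbers. The null stopping probability stays below that of a single-endpoint sign rule at every correlation short of 1.

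This does not threaten the validity of the final test. It is a weakness in interim protection, worth correcting because correction is cheap. The practical gain is small, because roughly three quarters or more of the patients are enrolled by then (103/134 = 77%; 109/134 = 81%).

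**What to change.** At the half-information look in section 13.1, where the stratified clustered log-rank test on local control is run anyway, add a non-binding futility criterion: consider stopping accrual if the estimated local-recurrence HR is 1 or more, whatever the iRR. In section 13.4, remove the clause that sends the trial to full accrual on iRR alone and keep iRR as supportive information.

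This needs wording changes only: no new data, no added look and no extra patients. Because the criterion is non-binding, the efficacy boundary and type I error are unaffected. The price is about a 3.5% chance of stopping when the true HR is 0.60, and power of about 88.8% instead of 90%. In return, stopping rises to about 50% under no effect and, under the event assumptions above, to about 90% to 97% at HR 1.67. At most about 25 patients would be spared at year 2.3 (31 if the decision were taken at month 26).

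If the sponsor prefers the two-condition rule, section 13.4 should describe it as an iRR sign rule with a local-control override, not simply as the Wieand rule, so that its lower chance of stopping is understood.
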